6.5.7 Pooling of Investigator Centers

The data from all study centers will be pooled together for the primary analyses. *No a priori* pooling strategy will be defined for this study. If after review of study data prior to planned interim analyses and final analyses the data review meeting identifies cohorts of sites that warrant pooling then a pooling strategy will be defined and implemented, and presented in the final CSR.

6.5.8 Determination of Baseline Values

Multiple baseline values for efficacy endpoints will be considered for the planned analyses. [Figure 1](#) presents an analysis map that highlights the various possible baselines for planned analyses. [Table 3](#) presents a dosing pathway matrix for all subjects enrolled in the study. Each pathway can be associated with a different baseline for analysis summaries and comparisons.

In order to examine the long term trends and changes in SA therapy for those subjects who roll-over from UX001-CL201 additional analyses will also be performed using baseline assessments obtained at the following time points ([Figure 1](#)):

- UX001-CL201 6/6 and 3/3 rollover subjects: UX001-CL201 Week 0 Visit
- UX001-CL201 0/6 and 0/3 rollover subjects: UX001-CL201 Week 24 Visit
- UX001-CL201 0/6 + 6/6 rollover subjects: UX001-CL201 Week 48 Visit
- UX001-CL201 0/3 + 3/3 rollover subjects: UX001-CL201 Week 48 Visit
- UX001-CL201 All rollover subjects: UX001-CL201 Week 48 Visit

- UX001-CL201 All rollover subjects: UX001-CL202 Part I Termination Visit
- UX001-CL202 Treatment Naïve Subjects: UX001-CL202 Part II Screening/Baseline Visit (Week 0: Note that protocol refers to this as week 12 on the T&E schedule.)

6.5.9 Coding of Events and Medications

Adverse events will be coded to standardize presentation of AEs and TEAEs. AEs will be mapped to the Medical Dictionary for Regulatory Activities (MedDRA Version 11.1) system for reporting (preferred term and body system).

Concomitant medications will be coded using WHO-DD (Drug Dictionary) (Version 2009003).

6.5.10 Analysis Software

Data manipulation, tabulation of descriptive statistics, calculation of inferential statistics, and graphical representations will be performed primarily using SAS (release 9.1.3 or higher) for Windows. If the use of other software is warranted, the final clinical study report will detail what software was used and for what purposes.

6.5.11 Analysis Data Sets

Analysis data sets will be developed for all study data in UX001-CL202. The analysis data sets will conform as close as possible to the CDISC Analysis Data Model (ADaM). Because this study also utilizes analysis data from the feeder study UX001-CL201 the final analysis data sets from this study will also be utilized to build, where appropriate, pooled analysis data sets with UX001-CL202. Subjects who roll over from the UX001-CL201 study into UX001-CL202 will carry with them the same USUBJID (Subject identifier) from UX001-CL201 for continuity of analysis data between studies.

6.6 Statistical Analysis: Disposition, Dosing, and Baseline Characteristics

6.6.1 Subject Disposition

The tabulation of number of subjects in each treatment group in both Part I (6g/day SA-ER) and Part II (12g/day SA-ER/SA-IR) and overall will be displayed for all subjects who are screened (Treatment Naïve Subjects: Part II), roll-over from UX001-CL201, in the Safety Population, and in the ITT Population, respectively.

The number and percent of subjects who completed or discontinued the study (at both the interim analysis and final analysis) will be displayed for each treatment group and overall together with reasons for early termination, where the percent is with respect to the total number of randomized subjects in that treatment group.

6.6.2 Dosing Summary

The number of doses administered will be summarized by treatment group for both the Safety and ITT Populations. Study medication dispensing and treatment compliance will be summarized in individual subject listings.

6.6.3 Demographics and Baseline Characteristics

Subject demographic data and baseline characteristics will be summarized descriptively by treatment group and overall. The demographic data and baseline characteristics will be summarized for both the Safety and ITT Populations.

Inclusion and Exclusion criteria will be presented in a listing.

6.6.4 Prior and Concomitant Medications

Concomitant medications will be assessed at all visits and throughout the course of the study.

Prior Medications: The number and percent of prior medications recorded for Treatment Naïve Subjects (enrolled directly into Part II) will be presented by the ATC class and preferred term as coded in the WHO-Drug dictionary (WHO-DD, version 200903). Prior medications will not be summarized for subjects who roll-over from UX001-CL201.

The number and percent of Concomitant Medications recorded for all subjects will be summarized by treatment group in Part I (6g/day SA-ER) and Part II (12g/day SA-ER/SA-IR) by the ATC class and preferred term as coded in the WHO-Drug dictionary.

Prior and concomitant medications will be summarized for the Safety Population.

6.7 Statistical Analysis: Clinical Efficacy

6.7.1 Planned Comparisons for Clinical Efficacy Parameters

The planned comparisons for UX001-CL202 are based on change from baseline assessments, where different baselines are utilized to evaluate treatment across a subject's treatment in

both UX001-CL201 and UX001-CL202. [Table 8](#) presents the planned comparisons for study data obtained in UX001-CL202 compared with study data from UX001-CL201 for roll-over subjects, as well as the treatment naïve subjects in UX001-CL202.

Clinical efficacy data collected in Part I of UX001-CL202 (all roll-over subjects dosed with 6g/day SA-ER) will not be included in planned comparisons for the clinical efficacy analysis.

Additional comparisons not specified in this statistical analysis plan may be completed as prospective analyses are completed to better understand study results. These additional comparisons will be clearly identified in final reporting.

Table 8 Planned Comparisons

Planned Comparison	Description
Primary Analysis #1: Week 24 12g/day SA/ER/SA-IR vs. Week 0	All subjects who roll-over from UX001CL201 will have their week 0 assigned as baseline (Part I termination visit of the 202 study) and the change from this score will be compared to the week 24 12g/day SA-ER/SA-IR treatment to assess the impact of the 12g/day SA-ER/SA-IR dose.
Primary Analysis #2: Week 24 12g/day SA/ER/SA-IR vs. Week 48 UX001-CL201 for 6/6+0/6 SA-ER	All subjects who roll-over from UX001CL201 will have their week 48 assigned as baseline and the change from this score will be compared to the week 24 12g/day SA-ER/SA-IR treatment to assess the impact of the 12g/day SA-ER/SA-IR dose across the combined 6/6+0/6 dose (UX001-CL201 subjects treated with 0/6 or 6/6 SA-ER will be combined for comparison from dosing pathways 1 and 3 from Table 3). A second comparison will be with a 6 minute walk test at Screening of ≥ 200 m (6MWT ≥ 200 m)
Primary Analysis #3: Week 24 12g/day SA/ER/SA-IR vs. Week 48 UX001-CL201 for 3/3+0/3	All subjects who roll-over from UX001CL201 will have their week 48 assigned as baseline and

Planned Comparison	Description
SA-ER	
the change from this score will be compared to the week 24 12g/day SA-ER/SA-IR treatment to assess the impact of the 12g/day SA-ER/SA-IR dose across the combined 3/3+0/3 dose (UX001-CL201 subjects treated with 0/3 or 3/3 SA-ER will be combined for comparison from dosing pathways 2 and 4 from Table 3)
 
A second comparison will be with a 6 minute walk test at Screening of ≥ 200 m (6MWT≥ 200m)

Secondary Analysis: Stability in endpoint over time and dose from Week 0 UX001-CL201 through Week 24 UX001-CL202. (Trend over time)
	
All subjects who roll-over from UX001CL201 will have their week 0 assigned as baseline and the stability from this baseline score will be assessed over time through the week 24 12g/day SA-ER/SA-IR treatment to assess the impact of dose combinations over time. For this analysis the UX001-CL201 subjects treated with 0/6 or 6/6 SA-ER will be combined for analysis from dosing pathways 1 and 3 and subjects treated with 0/3 or 3/3 SA-ER will be combined for analysis from dosing pathways 2 and 4 (Table 3). Each dosing pathway combination will be a separate analysis to assess the trend in endpoint scores over time and dose.
 
A second comparison will be with a 6 minute walk test at Screening of ≥ 200 m (6MWT≥ 200m)

Treatment Naïve Primary Analysis: Week 24 12g/day SA/ER/SA-IR vs. Week 0 Baseline (Week 12 on T&E)
	
Treatment Naïve subjects who enroll in UX001-CL202 will have a primary comparison of their change from baseline assessment for efficacy parameters.

Treatment Naïve Secondary Analysis: Week 24 12g/day SA/ER/SA-IR vs.
	
Treatment Naïve subjects in UX001-CL202

Planned Comparison	Description
Week 0-24 UX001-CL201 Placebo	endpoint data from week 0 to 24 will be compared to the UX001-CL201 Placebo (for those patients with 6MWT >=200m) treated subjects' endpoint data from week 0 to 24 for change from baseline assessments.

Additional comparisons may be defined upon review of the data to examine trends throughout a subject's treatment course through both UX001-CL201 and UX001-CL202, via the dosing pathways identified in [Table 3](#) and [Figure 1](#).

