The safety contact information for Ultragenyx (Biosoteria/Dohmen Safety) has been updated.

11. Drug Concentration Measurements.

Free SA in the urine will be measured in Part I of the study only. Free SA trough levels will be assessed in serum during Parts I and II of the study. There will be no assessments of free SA in the urine during Part II of the study.

Rationale: Results of PK assessments at the Week 24 interim analysis of the Phase 2 study (UX001-CL201) suggest serum SA measurement is more reliable than urine for characterizing trough levels of SA. Therefore, urine PK parameters will not be assessed in Part II of the study to avoid subjecting study participants to unnecessary procedures.

12. Statistical Methods.

An interim analysis will be conducted when the last subject has completed the Month 6 Visit of the Part II Treatment Period. For Part II efficacy evaluation of the continuing subjects, change from baseline of Part II to Month 6 assessment at 12g/day SA-ER/SA-IR dose will be determined and compared with the improvement observed during the first 6 months of treatment with 6g/day SA-ER dose and to the rate of change observed with placebo or 3g treatments during the first 6 months of the study. The 10 additional treatment naïve subjects will be evaluated for change from their baseline visit to Month 6 assessment at 12g/day SA-ER/SA-IR dose compared with placebo, 3 g and 6 g treatments for 24 weeks in subjects that walk more than 200m at baseline in the 6MWT.

Rationale: Changes to the planned statistical analysis are consistent with the modified study design to assess the efficacy and tolerability of the higher dose of sialic acid. The planned interim analysis following 6-months treatment with SA-ER/SA-IR will provide an initial assessment of safety and efficacy. If reasonable safety and efficacy are demonstrated, subjects will continue therapy for up to 36 months. Full details of planned analysis will be presented in the Statistical Analysis Plan for UX001-CL202.

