Part III: 12g/day dose – Each dose of SA-ER/SA-IR will consist of SA-ER tablets, each containing 500 mg of SA active ingredient in an extended release formulation and SA-IR capsules, each containing 500 mg of SA active ingredient. During the Part III Treatment Period, the 12,000 mg (12g) total daily SA dose will be administered by the oral route and will be divided into a TID or QID regimen. If tolerability issues arise, the dose may be temporarily stepped down until symptoms resolve.

6g/day dose – Each dose of SA-ER will consist of tablets, each containing 500 mg of SA active ingredient in an extended release formulation. During the Treatment Period, the 6000 mg (6g) total daily SA-ER dose will be administered by the oral route and will be divided into a TID regimen.

Part IV: 6g/day dose and 12g/day dose – Each dose of SA-ER will consist of tablets, each containing 500 mg of SA active ingredient in an extended release formulation. During the Treatment Period, the 6g total daily SA-ER dose will be administered by the oral route and will be divided into a TID

regimen. The 12g total daily SA-ER dose will be administered by the oral route and will be divided into a TID or QID regimen.

All doses should be taken with food (i.e. within 30 minutes following a meal or snack).

DURATION OF TREATMENT:

The Part I Treatment Period will be up to approximately 12 weeks (3 months) in duration. The Part II, Part III, and Part IV Treatment periods will be up to 36 months in duration. The total duration of the study will be up to 40 months.

CRITERIA FOR EVALUATION:

Efficacy:

Efficacy will be evaluated by continued improvement in clinical assessments. Efficacy assessments may differ depending on the phase of the study (i.e. Part I, Part II, Part III, or Part IV). For Part I efficacy evaluation, results from the last pre-treatment assessment from UX001-CL201 will be compared with the last post-treatment assessment for the Part I Treatment Period as listed in the Schedule of Events ([Table 2.1](#)), with efficacy conclusions based on change since SA-ER treatment initiation.

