An interim analysis will be conducted when a majority of subjects have completed the Month 6 Visit of the Part II Treatment Period. For Part II efficacy evaluation of the continuing subjects, change from baseline of Part II to Month 6 assessment at 12g/day SA-ER/SA-IR dose will be determined and compared with the improvement observed during the first 6 months of treatment with 6 g/day SA-ER dose, and to the rate of change observed with placebo or 3g treatments during the first 6 months of the study. The changes from baseline of the treatment-naïve subjects will be evaluated over time. In addition, changes in muscle strength over the entire treatment period of subjects who started with 6g/day and 3g/day will be evaluated and compared to the projected values of subjects who received placebo for the first 24 weeks of treatment in UX001-CL201.

Clinical Efficacy Measures:

- Hand-Held Dynamometry: Muscle strength based on the maximum voluntary isometric contraction (MVIC) against a hand-held dynamometer will be measured in the following muscle groups: gross grip, pinch, shoulder abductors, elbow flexors, elbow extensors, hip abductors, hip adductors, hip flexors, hip extensors, knee flexors and knee extensors. The total force (kg) will be measured as well as the percent of predicted normal force based on age, gender, height and weight (where applicable).
- Six-Minute Walk Test: The total distance walked (meters) in a six minute period will be measured as well as the percent of predicted normal distance based on age and gender.
- Walking Speed Test: The time required to walk 25 feet (7.62 meters) will be assessed at a comfortable and a maximum gait speed. The total number of seconds required for each speed will be recorded. Individual subject performance will also be compared to healthy peers based on normative data.
- Weighted Arm Lift Test: The number of times the subject can raise a 1 kg weight above the head in a 30-second period will be recorded. The test will be performed bilaterally.
- HIBM Functional Activities Scale: The total score, as well as subscale scores for mobility, self-care, and upper extremity function on an interview-administered functional disability measure will be recorded.

Exploratory Efficacy Measures:

- Serum protein markers: Serum specimens will be evaluated to assess potential use as biomarkers of sialylation.
- Creatine kinase levels in serum will be assessed as a potential biomarker for muscle injury

Safety:

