following approximately 12 weeks of treatment with 6g/day SA-ER and continue on to Part II of the study by crossing over to an increased daily SA dose of 12g/day. Since Part II of the study will be the first time GNE Myopathy subjects will be treated with the SA-ER/SA-IR investigational product, approximately 10 GNE Myopathy subjects will be enrolled to assess long-term safety and clinical efficacy of SA-ER/SA-IR in a treatment naïve population.

An interim analysis was conducted after 6 months of treatment with SA-ER/SA-IR; the results of this interim analysis have led to the establishment of Part III of the study. Part III will provide long-term safety and efficacy data on both 6 and 12g/day SA. This change is based on a review of individual subject data for the rollover subjects from the parent study UX001-CL201. The data analysis suggests that a small subset of subjects received an added benefit from the higher dose (defined as at least a 15% increase in either the UEC or LEC). The rollover subjects who met these criteria, along with the ongoing naïve subjects, had the option to remain on the 12g/day dose for the remainder of the study.

Part IV was added to change the formulation from SA-IR to SA-ER. The SA-IR dose formulation has been removed based on data showing that by the 4th day of dosing in a nonclinical study conducted in dogs, AUC for free SA was similar between the immediate and extended release formulations. In addition, a review of population data for Month 12 of Part III in the current study confirmed that 12g/day SA-IR did not appear to provide any additional benefit compared with 6g/day SA-ER, although some individual patients may have improved. Therefore, no further SA-IR will be administered after the initiation of Part IV; patients currently on 12g/day may continue receiving the 12g/day dose, if desired, by taking SA-ER.

Patients who elect to decrease from 12 g/day to 6 g/day may be allowed to do so upon Sponsor approval.

The 36-month treatment duration is intended to evaluate the long-term safety and efficacy of SA. While the lack of a control group may introduce difficulties in discerning natural disease progression from treatment effectiveness, due to the progressive debilitating nature of the disease, a placebo-controlled study of this duration is not feasible

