7.6.1.1 Clinical Efficacy Analyses

All subjects with any post-dose data will be included in the intent-to-treat (ITT) efficacy analysis.

Efficacy will be evaluated by continued improvement in clinical assessments. Efficacy assessments may differ depending on the phase of the study (i.e., Part I, Part II, Part III, or

Part IV). For Part I efficacy evaluation, results from the last pre-treatment assessment from UX001-CL201 will be compared with the last post-treatment assessment for the Part I Treatment Period as listed in the Schedule of Events ([Table 2.1](#)), with efficacy conclusions based on change since SA-ER treatment initiation. An interim analysis will be conducted when a majority of subjects have completed the Month 6 Visit of the Part II Treatment Period. For Part II efficacy evaluation of the continuing subjects, change from baseline of Part II to Month 6 assessment at 12g/day SA-ER/SA-IR dose will be determined and compared with the improvement observed during the first 6 months of treatment with 6 g/day SA-ER dose, and to the rate of change observed with placebo or 3g treatment during the first 6 months of the study.

The changes from baseline of the treatment-naïve subjects will be evaluated over time. Potential comparisons of the changes from baseline to Month 6 will be performed for the 6MWT, UE, and LE between the naïve group versus the placebo and 6g/day treatment groups for the first 24 weeks of treatments in subjects able to walk more than 200m at baseline. In addition, changes in muscle strength over the entire treatment period of subjects who started with 6g/day and 3g/day will be evaluated and compared to the projected values of subjects who received placebo for the first 24 weeks of treatment in UX001-CL201.

A full accounting of the analyses for Parts III and IV of the study will be provided in the Statistical Analysis Plan.

For those clinical evaluations with repeated assessments (i.e., HHD, 6 MWT, walking speed and weighted arm lift tests) the analysis will be performed using a repeated measures analysis. An exchangeable variance-covariance structure will be used. The final treatment effect estimate based on this model will be the estimated treatment difference at Month 36. The purpose of including data from assessments prior to Month 36 is to increase the precision of the estimated variance, while using categorical effects of time-by-treatment to avoid modeling assumptions.

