1 INTRODUCTION

This document presents a statistical analysis plan (SAP) for Ultragenyx Pharmaceutical, Inc. Protocol UX001-CL202 (*An Open-label Phase 2 Extension Study to Evaluate the Long Term Safety and Efficacy of Sialic Acid-Extended Release (SA-ER) Tablets and Sialic Acid-Immediate Release (SA-IR) Capsules in Patients with GNE Myopathy or Hereditary Inclusion Body Myopathy*).

Reference materials for this statistical plan include the Protocol UX001-CL202 (Original: 01 March 2013, Amendment #1: 02 October 2013), UX001-CL202 Case Report Forms (24 July 2013), feeder study Protocol UX001-CL201 and the SAP for UX001-CL201 (05 November 2013: Week 48 Analysis). Study UX001-CL202 is an Open-Label extension study and treatment is not blinded. Subjects completing 48-week in study UX001-CL201 are eligible to continue treatment under this open-label extension protocol testing an increased dose of SA. Additional GNE Myopathy subjects will be enrolled to assess the safety and efficacy of SA-ER/SA-IR in a treatment naïve population. Ultragenyx Pharmaceutical is conducting UX001-CL202 in two parts:

- Part I of the study will provide additional information on the long-term safety and efficacy of 6g/day SA ER;
- Part II of the study will assess the safety and efficacy of 1.5 g of SA-ER / 1.5 g of SA-IR treatment 4 times per day (12g/day SA-ER/SA-IR total dose) for 6 months. If reasonable efficacy and safety are demonstrated at the interim analysis at 6 months post initiation of part II, the subjects may continue therapy for up to 36 months.

The statistical plan described hereafter is an *a priori* plan. The SAP will be finalized and approved prior to completing inferential or descriptive analyses of data pertaining Ultragenyx Pharmaceutical, Inc. Protocol UX001-CL202. Statistical Analysis programming may occur as study data accumulate in order to have analysis programs ready at the time the study finishes. For the reasons stated herein the conduct of the study in the field is considered to be independent of any study outcome that might materialize upon enactment of the currently proposed statistical analysis plan.

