6.5.1 Changes in Analysis in Comparison to Study Protocol

The analyses described in this analysis plan are consistent with the intended analyses described in the study protocol. In addition results from the UX001-CL201 study, both the Week 24 and Week 48 analyses, will be utilized as baseline information to explore and compare the various dosing combinations and trends in efficacy parameters, between the UX001-CL201 randomized feeder study and the UX001-CL202 extension study.

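### No rollover row of SAP Table 8 defines the protocol's Month 6 comparison of 12 g with 6 g, placebo or 3 g: Primary #1 has no comparator, and Primary #2 and #3 can mix 6 g with 12 g

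*SAP*

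**What the plan says.** Protocol 7.6.1.1 takes the change on 12 g from Part II baseline to Month 6 in continuing subjects and says it will be "compared with the improvement observed during the first 6 months of treatment with 6 g/day SA-ER dose". The Synopsis has the same plan and adds the second comparator: "and to the rate of change observed with placebo or 3g treatments during the first 6 months of the study".

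SAP section 1 cites the protocol up to "Amendment #1: 02 October 2013". The protocol's summary of that amendment, under Statistical Methods, already has the comparison: "change from baseline of Part II to Month 6 assessment at 12g/day SA-ER/SA-IR dose will be determined and compared with the improvement observed". The gap is therefore not explained by the SAP resting on an older protocol version.

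SAP Table 8 (6.7.1) has four rows for rollover subjects:

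- **Primary #1:** baseline is the Part I termination visit and the endpoint is Week 24 on 12 g.
- **Primary #2** (6/6 and 0/6 pooled) and **Primary #3** (3/3 and 0/3 pooled): subjects "will have their week 48 assigned as baseline and the change from this score will be compared to the week 24 12g/day SA-ER/SA-IR treatment". Week 48 here is the CL201 visit.
- **Secondary:** a trend from CL201 Week 0, run separately in each of the same two pools.

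SAP 6.5.1 describes the planned analyses as "consistent with the intended analyses described in the study protocol".

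**The concern.** SAP 6.3 makes the Month 6 analysis the primary one for efficacy, and SAP 1.3 lists as an exploratory objective whether 12 g/day does better than the earlier SA-ER treatment. A change from own baseline cannot answer that in a progressive disease. A dose that slows decline can still show a negative change, and a dose that adds nothing shows the background decline. Primary #2 and #3 have a further problem: both are described as measuring the effect of 12 g, yet their window can include time on 6 g. An analyst who follows Table 8 exactly would produce p-values for rollover subjects, none of which estimates 12 g against 6 g, placebo or 3 g.

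**Working it through.** The study is not powered (SAP 6.1), so there is no sample-size figure to reproduce. The check sets each row against the protocol comparison and then sizes the difference.

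**Rows against the protocol contrast**

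| Row | Interval | Treatment in the interval | Comparator change |
|---|---|---|---|
| Protocol, continuing subjects | Part II baseline to Month 6 | 12 g | First 6 months on 6 g; placebo or 3 g |
| Primary #1 | Part I termination to Week 24 | 12 g | None |
| Primary #2 | CL201 Week 48 to Week 24 on 12 g | 6 g, then 12 g | None; the reference is a visit score |
| Primary #3 | As #2 | 6 g, then 12 g, after 3 g in CL201 | None; the reference is a visit score |
| Secondary | CL201 Week 0 to Week 24 on 12 g | All, pooled | None; trend only |

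None of the four rows defines the contrast. The only Table 8 row that sets 12 g against a separate 24-week reference period is the treatment-naïve secondary row, which uses placebo.

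**Share of the Primary #2/#3 window on 6 g.** The Synopsis says: "The Part I Treatment Period will be up to approximately 12 weeks (3 months) in duration". The Figure 1 footnote in the SAP says that some subjects skipped Part I. With p weeks in Part I, the window is 24 + p weeks and the share on Part I 6 g is p/(24 + p):

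- p = 0: 24 weeks, 0%
- p = 6: 30 weeks, 6/30 = 20%
- p = 12: 36 weeks, 12/36 = 33%

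If Month 6 is taken as 26 weeks, the last two shares become 6/32 = 18.8% and 12/38 = 31.6%.

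**Illustration.** Assume a linear decline of d per 24 weeks on 6 g; the documents give no value for d.

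| Quantity | 12 g adds nothing | 12 g halves decline |
|---|---|---|
| Primary #1 | -1.0d | -0.5d |
| Primary #2, p = 0, 6, 12 | -(24+p)/24 d = -1.0d, -1.25d, -1.5d | -(0.5+p/24) d = -0.5d, -0.75d, -1.0d |
| Protocol contrast | -1.0d - (-1.0d) = 0 | -0.5d - (-1.0d) = +0.5d |

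The two Primary #2 ranges meet at -1.0d. A dose with no added benefit and no Part I gives the same value as a halved decline after a full Part I.

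Rescaling #2 to 24 weeks does not repair it. With decline halved, the rescaled decline is (12+p)/(24+p) d = 0.50d, 0.60d, 0.667d. The share of the true slowing recovered is (1 - that value)/0.5 = 100%, 80%, 67%.

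**Secondary row, if read as a before/after comparison.** Let w be the share of the pool that took placebo in Weeks 0-24, and k the placebo decline relative to 6 g; both are assumed. The pooled first-24-week decline is wk + (1 - w).

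- w = 1/3, k = 1.5: 1.17d
- w = 2/3, k = 2: 1.67d

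A 12 g period that adds nothing over 6 g would then look 0.17d to 0.67d better. At k = 1 the artefact is zero.

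**Precision of the missing contrast.** The 95% CI half-width, in SDs of the within-subject difference, is t(0.975, n-1)/√n. Pathway sizes are not given, so n is assumed:

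- 6 g contrast: n = 15 gives 0.55, n = 30 gives 0.37
- Placebo or 3 g contrast: n = 8 gives 0.84, n = 20 gives 0.47

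**The case against.** The strongest reply is that the comparison is present but badly worded. The lead-in to Table 8 speaks of comparing CL202 data with CL201 data, and the GEE model in SAP 6.7.2 has a term for a comparator dose and describes treatment coefficients as mean differences in change from baseline. On that reading, Primary #2 is 12 g against 6 g. But 6.7.2 refers back to Table 8 for the comparisons, calls its estimate a test of change from baseline, and adds the two treatment terms in its sample ESTIMATE statement. The row text makes Week 48 the baseline. Even on the generous reading, the 24 weeks before that visit are the first 6 months on 6 g only for 0/6 subjects, not for 6/6.

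Other SAP text comes close. Section 6.5.8 commits to treatment-start baselines, and 6.7.6 commits to a before/after look at rates for the HHD composites. Sections 5.1 and 6.7.7 to 6.7.12 allow comparisons with the prior period as options. None names the contrast. Figure 1, the map of baselines, is not available for this review and might add detail on baselines, but it would not change what the Table 8 rows say.

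Several limits do stand:

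- The protocol calls its section 7.6 a guide, the objective is exploratory, and the lack of a control group is disclosed.
- The Part III dosing change rested on individual responses against a 15% criterion, not on Table 8 p-values.
- The protocol's Synopsis describes strength in CL201 as stabilised. If strength did not change during Part I, Primary #2 has no mixing effect.
- The Secondary-row figure sizes a contrast that the SAP does not plan.
- The protocol contrast is zero under no added benefit only if the slope on 6 g is constant. If an early response to 6 g fades, the contrast is biased against 12 g.

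**Conclusion.** The concern holds and should be fixed. That none of the four rollover rows defines the protocol comparison follows from the text and needs no assumption. The mixing in Primary #2 and #3 covers 0 to 33% of the window, depending on time in Part I. The multiples of d are illustrations that rest on an assumed linear decline, and they vanish at d = 0. This is more than missing detail, because a correct run of Table 8 cannot address the stated objective for rollover subjects. The exploratory status and lack of power limit the consequence, so an estimate with its interval is what is needed, not a powered test.

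**What to change.** 1. Add to Table 8, for pathways 1 and 3, the within-subject difference: the Part II baseline to Month 6 change on 12 g, minus the first 24-week change on 6 g (CL201 Weeks 0-24 for 6/6, Weeks 24-48 for 0/6), with a 95% CI.
2. Add contrasts of the 12 g change with placebo Weeks 0-24 (within-subject in pathways 3 and 4) and with 3 g Weeks 0-24 (within-subject in pathway 2). Label any use of other pathways as between-subject.
3. For 12 g effects, use the last assessment before the first 12 g dose as baseline. Reconcile the rollover Week 48 baselines in SAP 6.7.11 to 6.7.13 with Primary #1. State that the exclusion of Part I efficacy data in 6.7.1 does not cover the Part I termination visit, which is also the Part II baseline. Nothing changes for treatment-naïve subjects.
4. Label Primary #2 and #3 as supportive analyses over a mixed-dose period, and correct 6.5.1.
5. For rows with a comparator dose, write the ESTIMATE statement as 12 g minus comparator with matching visit terms. The sample code's three terms also do not match the two-coefficient sum in the text.
6. Label the added contrasts as defined after the Month 6 data were seen, since Protocol 7.2 reports: "An interim analysis was conducted after 6 months of treatment with SA-ER/SA-IR".

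The cost is SAP wording and programming; no new data are needed. SAP 6.5 says the SAP will not be amended for post-hoc analyses. If it is not reopened, the contrasts can go into the study report with that label. The report should also say that the 6 g contrast leaves out pathways 2 and 4 (whose first 6 g exposure is Part I, at most about 12 weeks), that it is confounded with calendar time and disease progression, and that it is unpowered.
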